5 STUDY SCHEDULE

The study consists of a Pre-screening Period, a Screening Period, a Treatment Period, an Efficacy and Safety Follow-up Period (Final Study Visit), plus Survival Follow-up. Informed consents (one for Pre-screening and a second one for the main study after the confirmation of CD30-expression) must be obtained using the current, approved versions of the ICF prior to commencing Pre-screening and Screening, respectively. Subjects will undergo a Pre-screening for CD30 expression up to 28 days before Screening and, if confirmed, will start Screening assessments up to 21 days before receiving the first dose of AFM13. Due to the nature of the diseases being studied, Screening assessments may, in practice, be carried out over a shorter time-period. The Efficacy and Safety Follow-up Period (Final Study Visit) assessments may be conducted between 30 to 37 days after the subject has permanently discontinued AFM13 study drug; however, a final AE and concomitant medication review must take place 30 days after the last dose of AFM13. Where applicable, disease progression and survival status will be checked every 3 months by telephone interview, or during the subject's routine clinic visits, following completion of the Final Study Visit assessments.

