8.6.1.2 Duration of Response

The DOR defined as time from first assessment of PR or CR to the first assessment of progressive disease will be summarized by descriptive statistics including median DOR and respective 95% CIs and Kaplan-Meier estimates. DOR will also be listed.

Subjects who started a new anti-lymphoma therapy prior to a documented progressive disease (PD) will be censored at the last disease assessment prior to initiation of new anti-lymphoma therapy. Detailed censoring rules will be described in the SAP.

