3 STUDY DESIGN

3.1 General study design

This is an open-label, multicenter, Phase 2 study in subjects with R/R CD30-positive PTCL and TMF.

Subjects with PTCL will be enrolled to Cohort A or B based on the centrally determined CD30 expression level detailed below:

- Subjects with $\geq 10\%$ CD30 expression for Cohort A
- Subjects with $\geq 1\%$ to $< 10\%$ CD30 expression for Cohort B

[figure not shown]
After the planned Interim Analysis (IA), Cohorts A and B may be combined with the CD30 positivity defined as $\geq 1\%$ by centrally assessed IHC.

Subjects with TMF and centrally determined $\geq 1\%$ CD30 expression will be enrolled to Cohort C.

The study targets to investigate the antitumor activity and safety of AFM13 dosed weekly at 200 mg until disease progression, unacceptable toxicity, Investigator discretion or withdrawal of consent.

The Study Flow Chart is presented in Figure 1.

Figure 1: Study Flow Chart

Abbreviations: CD = cluster of differentiation; IHC = immunohistochemistry; PTCL = peripheral T-cell lymphoma; R/R = relapsed/refractory; TMF = transformed mycosis fungoides.

Final Analysis Statistical Analysis Plan (SAP)

All subjects enrolled may participate in the following study periods:

- Pre-screening period (up to 28 days prior to starting the screening period).
- Screening period (up to 21 days prior to first dose of AFM13).
- Treatment period.
- Efficacy and Safety follow-up period (30 to 37 days from last dose of AFM13).
- Survival follow-up (after completion of the study) every three months after Final study visit (+/- 1 month).

Subjects will undergo study assessments from the Screening period to the Efficacy and Safety follow-up period at scheduled site visits. All subjects are considered “on study” until they complete the Efficacy and Safety follow-up period, withdraw consent, are lost to follow up, or die.

A subject is considered to have completed the study if the subject has either a disease progression or died or completed the Efficacy and Safety follow-up or when the subject has at least a partial response/remission and gets transitioned to a transplant.

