Progression (as determined by Investigator)	Date of progression (as determined by Investigator)	Event
Death due to any cause	Date of death	Event
PD (as determined by Investigator) or death after 1 missed assessment (ie, \geq 59 days between 2 assessments until Cycle 4, \geq 87 days from Cycle 5 and \geq 122 days from Survival Follow-up)	Date of PD (as determined by Investigator) or death	Event
PD (as determined by Investigator) or death after 2 or more missed assessments (ie, \geq 118 days between 2 assessments until Cycle 4, \geq 174 days from Cycle 5 and \geq 244 days from Survival Follow-up)	Date of last disease assessment or date of last survival contact (for Survival Follow-up) before missed assessments	Censored
No baseline tumour assessment	Date of first study drug	Censored
No post-baseline response assessment	Date of first study drug	Censored
Start of new anti-cancer therapy before progression (as determined by Investigator) or death	Date of last disease assessment or date of last survival contact (for Survival Follow-up) prior to new anti-cancer therapy *	Censored

Final Analysis Statistical Analysis Plan (SAP)

Event	Event or censored date	Event or censored
Transplant before progression (progression as determined by Investigator) or death or start of new anti-cancer therapy	Date of last disease assessment or date of last survival contact (for Survival Follow-up) prior to date of transplant	Censored
No progression determined by Investigator or death	Date of last disease assessment or date of last survival contact (for Survival Follow-up)	Censored

Note: Only disease assessments recorded in the CRF are included in the analysis.

* The new anti-cancer therapy information is only collected on the “Survival follow-up” page but no date is collected. Consequently, it is assumed that the new therapy starts between the follow-up where the question “Did the patient start any new anti-cancer therapies?” is “Yes” and the previous follow-up. The subject will be censored at the last disease assessment prior or on this previous visit.

Final Analysis Statistical Analysis Plan (SAP)

[REDACTED]

[REDACTED]	[REDACTED]	[REDACTED]
[REDACTED]	[REDACTED]	[REDACTED]
[REDACTED]	[REDACTED]	[REDACTED]
[REDACTED]	[REDACTED]	[REDACTED]
[REDACTED]	[REDACTED]	[REDACTED]
[REDACTED]	[REDACTED]	[REDACTED]
[REDACTED]	[REDACTED]	[REDACTED]
[REDACTED]	[REDACTED]	[REDACTED]
[REDACTED]	[REDACTED]	[REDACTED]
[REDACTED]	[REDACTED]	[REDACTED]

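### SAP Table 3 lets Investigator DOR be censored at a survival contact: the new-therapy row contradicts its own footnote and the protocol, and three other rows credit response time without a disease assessment

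*SAP*

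**What the plan says.** SAP 8.6.2 derives DOR separately for the IRC (censoring Table 1) and the Investigator (Table 3). Table 1 censors at the last disease assessment whenever a post-baseline assessment exists. Table 3 adds the last survival contact as an alternative in four rows:

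- PD or death after two or more missed assessments
- new anti-cancer therapy
- transplant
- no PD and no death

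The last of these reads "Date of last disease assessment or date of last survival contact (for Survival Follow-up"). The new-therapy row reads "Date of last disease assessment or date of last survival contact (for Survival Follow-up) prior to new anti-cancer therapy" and carries a footnote that ends: "The subject will be censored at the last disease assessment prior or on this previous visit". A general note under the table adds: "Only disease assessments recorded in the CRF are included in the analysis".

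Protocol 8.6.1.2 fixes one censoring case. Subjects who start new therapy before PD "will be censored at the last disease assessment prior to initiation of new anti-lymphoma therapy". For the rest it says: "Detailed censoring rules will be described in the SAP".

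On the contacts, Protocol 5 states that "disease progression and survival status will be checked every 3 months by telephone interview", or alternatively at routine clinic visits. SAP 3.1 schedules them "every three months after Final study visit (+/- 1 month").

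**The concern.** A Lugano or Olsen response is established by a disease assessment. A telephone contact can report that nobody has diagnosed progression, but it cannot show that a CT-based or PET-based response persists. SAP 8.6.2 reports DOR separately for those two modalities, yet one contact date could extend both curves.

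Two things are at stake. In the new-therapy row a programmer is given two different dates for the same subject. In the other rows, Investigator and IRC DOR would differ partly because their censoring rules differ and not because the readers disagree. Investigator DOR is also reported at 3, 6, 9 and 12 months and beyond, and by subgroup, so the effect spreads past the median.

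**Working it through.** **1. The four rows side by side**

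| Row | Table 1 (IRC) | Table 3 (Investigator) | Protocol 8.6.1.2 |
|---|---|---|---|
| New therapy | last disease assessment | assessment or contact; footnote: assessment only | last disease assessment |
| Two or more missed | last disease assessment | assessment or contact | left to SAP |
| Transplant | last disease assessment | assessment or contact | left to SAP |
| No PD or death | last disease assessment | assessment or contact | left to SAP |

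Only the first row conflicts with the protocol. The conflict is not marginal there: the footnote says that new therapy is recorded only on the Survival Follow-up page, so every subject in that row is in the phase where the contact option applies.

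**2. Is the contact option deliberate?** Table 3's missed-assessment limits reproduce as follows:

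- until Cycle 4: 8 × 7 + 3 = 59 days, doubled 118
- from Cycle 5: 12 × 7 + 3 = 87 days, doubled 174
- Survival Follow-up: (3 + 1) months × 30.44 = 121.75, rounded to 122 days, doubled 244

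The third pair exists only in Table 3. Contacts are therefore treated as assessments on purpose, which does not sit well with the note that only disease assessments enter the analysis.

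**3. Unimaged time per subject.** One contact falls 2 to 4 months after the Final Study Visit: 61 to 122 days. The Final Study Visit is 30 to 37 days after the last dose (SAP 3.1).

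- If a disease assessment is done at the Final Study Visit, one contact adds 61 to 122 days.
- If the last scan was 12 weeks before the last dose (assumption), the maximum is 84 + 37 + 122 = 243 days.
- With four contacts under the same assumption, the last falls up to 396 days after the visit: 84 + 37 + 396 = 517 days.

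In the new-therapy row, take a subject with no new therapy at contact 1 and new therapy reported at contact 2. The row permits censoring at contact 1, while the footnote sends the date back to the last scan. The two dates differ by the amounts above.

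**4. Direction.** The Kaplan-Meier estimate is the product over event times of (1 − d/n), where d is the number of events and n the number at risk. Moving a censor date later leaves every d unchanged and can only raise n at the event times in between. No factor falls, so neither the curve nor the median can fall.

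**5. Illustrative size.** All inputs here are assumptions: 35 responders; exponential DOR with median 90, 180 or 365 days (3.0, 5.9, 12.0 months); median time to stopping scans without detected PD 120 days (early) or 365 days (late); contacts every 91 days that detect existing PD with probability 0, 0.5 or 1; median PD to death 180 days; 24 months of follow-up; 300 data sets in each of 18 settings.

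Kaplan-Meier median in months:

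| True median, stopping | Detection | Table 3 as written | Censor date moved, events unchanged | Table 1-type rule |
|---|---|---|---|---|
| 3.0, late | 0, 0.5 or 1 | 3.7 | 3.7 | 3.7 |
| 5.9, early | 0 | 11.7 | 9.3 | 6.4 |
| 5.9, early | 0.5 | 9.0 | 8.3 | 6.4 |
| 5.9, early | 1 | 7.6 | 7.3 | 6.4 |
| 12.0, early | 0 | 19.6 | 13.0 | 12.0 |
| 12.0, early | 1 | 13.3 | 10.6 | 11.3 |

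Comparing the first two rules over all 18 settings, the gap runs from 0 to 19.6 − 13.0 = 6.6 months, and none of the 18 × 300 = 5,400 data sets showed a fall. The last column also censors PD or death that comes too long after the last scan (118 or 174 days). Against that rule Table 3 usually gave the longer median, but it gave the shorter one in 0 to 21% of data sets per setting, so the one-way direction in step 4 holds only with events fixed.

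**6. Events matter too.** In the final row of the table, moving only the censor date gives 10.6 months against a true 12.0. PD learned at a contact still counts, while a contact reporting no PD earns no time. Changing censoring alone replaces one bias with another.

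**The case against.** A reader might infer that Table 3 contradicts the protocol's censoring rule throughout, that it replaces assessments with telephone calls, and that reported DOR is inflated in general. The documents do not support this.

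- The protocol sets a censor date only for new therapy and leaves the rest to the SAP. The no-PD/no-death row contradicts nothing in it.
- Table 3 says or, not instead of, and limits the contact date to Survival Follow-up.
- Contacts ask about progression as well as survival, and may be clinic visits.
- Subjects who stop treatment because of CR remain on study with scheduled assessments (Protocol 3.6), and those who withdraw consent have no follow-up. The affected group is smaller than all responders who stop without PD.
- The DOR secondary endpoint in SAP 4.2 and Protocol Table 2 is IRC-based and uses Table 1.
- Protocol 5.1.3, 5.1.4 and the schedule of assessments, and the text of SAP section 9, are redacted. What a follow-up contact involves, and whether this rule is declared as a change, cannot be seen.

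All of this stands and limits the point. It does not remove the mismatch between the new-therapy row, its footnote and the protocol, or the difference between Tables 1 and 3. It is also fair that treating contacts as assessments for both events and censoring is internally consistent. That is a reason to keep it as a sensitivity analysis, not as the main rule beside an IRC analysis built differently.

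**Conclusion.** The new-therapy row is an error as written and must be reconciled with its footnote and Protocol 8.6.1.2. In the other three rows the contact date is a questionable choice, not a contradiction of the protocol: it credits time without a recorded disease assessment and makes Investigator DOR not comparable with IRC DOR.

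The direction, longer or unchanged, is certain only with events held fixed. The size cannot be taken from the documents. The illustrative range of 0 to 6.6 months in the median depends on how early scans stop and how well contacts detect PD, and it is nil or small when few subjects stop early or contacts detect PD reliably. The consequence is confined to supportive Investigator DOR.

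**What to change.** 1. In Table 3's new-therapy row, censor at the last disease assessment before new therapy, as its footnote and the protocol require.
2. In the two-or-more-missed, transplant and no-PD/no-death rows, censor at the last disease assessment. Apply the same standard to events: PD reported only at a survival contact, with no recorded disease assessment, does not count in the main Investigator analysis. Align the 122/244-day limits accordingly, so that gaps in the main analysis run between disease assessments.
3. Keep the contact-based version as a labelled sensitivity analysis, with contact-reported PD as events and contact dates as censor dates, and with the 122/244-day limits.
4. Check the Investigator table for the COVID analysis set (Table 4), whose rows are not legible in the public copy, for the same wording.

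The cost is SAP wording and one extra sensitivity run; no new data are needed. Any scan recorded as a disease assessment during follow-up still counts. The downside is somewhat less follow-up and possibly fewer late events in Investigator DOR.

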8.6.3 Analysis of exploratory endpoints

[REDACTED]

[REDACTED]

[REDACTED]

[REDACTED]

[REDACTED]

[REDACTED]

[REDACTED]

[REDACTED]

[REDACTED]

[REDACTED]

Final Analysis Statistical Analysis Plan (SAP)

[REDACTED]

8.7 Safety analyses

Safety analyses will be conducted on the safety set and will be performed for all safety variables specified below.

All the data will be summarized by cohort, and cohorts A and B combined.

No statistical test will be performed.

8.7.1 Adverse events

All Adverse events (AEs) will be classified by SOC and PT according to the MedDRA Version 22.0 or higher.

AEs will be graded according to the National Cancer Institute Common Terminology Criteria for Adverse Events (NCI CTCAE) version 5.0.

In summaries by SOC and/or PT, adverse events will be sorted by decreasing frequency within each SOC and/or PT according to the highest subject number in Cohort A.

AEs will be classified as pre-treatment AEs or treatment-emergent adverse events (TEAEs) defined as follows:

Pre-treatment AE: any AE that started after study enrollment (ICF signed) and before the first dose date of study medication.

TEAE: any AE that was newly developed at or after the first dose date of study drug.

Related AE: AE will be defined as related if causality is either ‘definitely related’, ‘probably related’, ‘possibly related’ or missing.

Details for imputing missing or partial start dates of adverse events are described in section 7.2.2.

AE summary tables listed below will be presented:

- All TEAEs.
- All related TEAEs.
- TEAEs by maximum severity.

Final Analysis Statistical Analysis Plan (SAP)

- Serious TEAEs.
- Non-serious TEAEs.
- Related serious TEAEs.
- Related TEAEs by maximum severity.
- TEAEs with NCI CTCAE grades ≥ 3 .
- Related TEAEs of NCI CTCAE grades ≥ 3 .
- Important medical events (IMEs) (IMEs include only TEAEs):
 - Infusion-related reactions (IRRs).
 - Hepatic TEAEs (selecting events within “Drug related hepatic disorders - comprehensive search” Standardized MedDRA Queries (SMQ)).
 - Other IMEs (ie, SAEs with “Other important medical event” reason).
- Frequency of IRRs by maximum severity and visit.
- TEAEs leading to interruptions or modifications of study drug (action taken as “Drug reduced”, “Drug interrupted”, Drug delayed”, “Treatment held”).
- TEAEs leading to premature discontinuation of study drug (action taken as “Drug discontinued”).
- AEs leading to death.
- Related AEs leading to death.
- Frequent non-serious TEAEs (SOCs or PTs with at least 5% of subjects within the cohort).
- Glucocorticoid/Corticosteroid premedications (Yes/No) and frequency of IRR by maximum severity and visit.

All AEs will be summarized by MedDRA SOC, PT and cohort using frequency counts and percentages (ie, number and percentage of subjects with an event). In addition, an overall summary for the categories above will be prepared by cohort.

Where a subject has the same adverse event, based on SOC and/or PT, reported multiple times, the subject will only be counted once at the SOC and/or PT level in adverse event frequency tables.

When reporting adverse events by severity, in addition to providing a summary table based on the event selection criteria detailed above, summary table will also be provided based on the most intense event regardless of the relationship to study treatment.

Final Analysis Statistical Analysis Plan (SAP)

IRR will be summarized by visit and cohort. But IRRs are collected during the study without being linked to a specific visit. Consequently, the following rule will be used to assign the IRRs to a visit:

If study drug administration at Cycle X Day Y \leq IRR start date/time \leq study drug administration at Cycle X Day Y + 24 hours then the visit is assigned to Cycle X Day Y; else visit is assigned to Unscheduled (Unscheduled visit should be also included in the “by visit” table).

8.7.2 Clinical laboratory evaluations

For the purposes of summarization in both the tables and listings, all laboratory values will be presented in standard units.

Laboratory results will be graded by NCI CTCAE version 5.0. For the tests without grading, only the classification according to normal ranges will be done.

Hematology (including coagulation), chemistry and urinalysis will be summarized by cohort, visit and parameters in each category.

If a lab value is reported using a nonnumeric qualifier eg, less than (<) a certain value, or greater than (>) a certain value, the given numeric value will be used in the summary statistics, ignoring the nonnumeric qualifier. This will be explained in the footnotes of the respective outputs.

Descriptive statistics for actual measurement and change from baseline at scheduled visits will be performed.

Urinalysis parameters will be also summarized by frequency counts by cohort and for each scheduled visit for nonnumeric parameters.

Shift tables for CTCAE grades and normal ranges from baseline to each visit and to worst post-baseline visit will be presented.

All laboratory tests will be listed. A separate listing for abnormal lab values (\geq Grade 3, and low/high values) will be presented.

Liver and renal events

The subjects with liver events at any post-baseline visit will be summarized and listed for the following categories:

- ALT or AST $> 3 \times$ upper limit of normal (ULN).
- Alkaline phosphatase (ALP) $> 2 \times$ ULN.
- Total bilirubin $> 2 \times$ ULN.
- (ALT or AST $> 3 \times$ ULN) and total bilirubin $> 2 \times$ ULN and ALP $> 2 \times$ ULN.

Final Analysis Statistical Analysis Plan (SAP)

- LDH > 2 x ULN.
- Albumin < lower limit of normal (LLN).

Glomerular filtration rate (GFR) in mL/min/1.73 m² will be summarized and listed at each visit and to worst post-baseline visit with the following categories: <15, [15-30[, [30-45[, [45-60[, [60-90[and ≥ 90.

GFR values will be derived using Chronic Kidney Disease Epidemiology Collaboration (CKD-EPI) equation:

$$GFR = 141 \times MIN \left(\frac{Creat}{K}, 1 \right)^\alpha \times MAX \left(\frac{Creat}{K}, 1 \right)^{-1.209} \times 0.993^{Age} \times 1.018 [if Female] \times 1.159 [if Black or African American]$$

where

Creat is serum creatinine in μmol/L

K is 61.9 for females and 79.6 for males

α is -0.329 for females and -0.411 for males.

[REDACTED]

[REDACTED]

[REDACTED]

[REDACTED]

[REDACTED]

[REDACTED]

[REDACTED]

[REDACTED]

[REDACTED]

[REDACTED]

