A total of 30 patients (12 in Part 1 [dose escalation] and 18 in Part 2 [extension study]) were analyzed for safety and efficacy; 10 patients completed all 52 weeks of study drug.

The maximum tolerated dose was not exceeded and the minimal activation dose was determined to be 7 mg/kg. Overall, all 30 patients experienced at least one treatment emergent adverse events (TEAEs). The most frequently reported events by preferred terms (PTs) were infusion related reaction (28 [93.3%] patients), nausea (12 [40.0%] patients), pyrexia (12 [40.0%] patients), diarrhea (10 [33.3%] patients), rash (10 [33.3%] patients), upper respiratory tract infection (9 [30.0%] patients), cough (8 [26.7%] patients), fatigue (8 [26.7%] patients), headache (7 [23.3%] patients), pruritus (7 [23.3%] patients), alanine aminotransferase increased (6 [20.0%] patients), and vomiting (6 [20.0%] patients).

The ORR was 83.3% (25/30 patients) with 95% CI of 65.3, 94.4. CR was observed in 11 (36.7%) patients and partial response was observed in 14 (46.7%) patients: Stable disease was observed in 2 (6.7%) patients and progressive disease was observed in 10.0% (3 patients).

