8.6.2.2 Safety Laboratory

Safety laboratory results will be graded by NCI CTCAE version v5.0 (or higher). If no grading exists values will be classified into low/normal/high based on laboratory normal ranges. Each parameter will be presented by descriptive statistics at each visit including change from baseline (Screening). Shift tables for CTCAE grades and normal ranges will be presented. All laboratory values will be listed. A separate listing for abnormal lab values (\geq Grade 3, and low/high values) will be presented.

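### The only combined liver category also requires raised ALP, so the summary table cannot show how many subjects had ALT/AST above 3 x ULN together with bilirubin above 2 x ULN

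*SAP*

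**What the plan says.** SAP 8.7.2, under the sub-heading on liver and renal events, introduces its list thus: "The subjects with liver events at any post-baseline visit will be summarized and listed for the following categories". Six categories follow:

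1. ALT or AST above 3 x ULN
2. ALP above 2 x ULN
3. total bilirubin above 2 x ULN
4. ALT or AST above 3 x ULN combined with "total bilirubin $> 2 \times$ ULN and ALP $> 2 \times$ ULN"
5. LDH above 2 x ULN
6. albumin below LLN

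Only category 4 combines parameters. The published list shows no redaction between its lead-in and the GFR text; the blacked-out blocks come after the GFR formula.

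Other planned outputs that bear on the liver:

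- SAP 8.7.2 also plans descriptive statistics by visit and "Shift tables for CTCAE grades and normal ranges from baseline to each visit and to worst post-baseline visit will be presented". Protocol 8.6.2.2 is the parent text: "Shift tables for CTCAE grades and normal ranges will be presented".
- On listings, SAP 8.7.2 says: "All laboratory tests will be listed. A separate listing for abnormal lab values".
- SAP 8.7.1 has a table of hepatic TEAEs, selected by a standardized MedDRA query and treated as important medical events. Protocol 5.4.7 has the investigator record clinically significant laboratory findings as AEs when they represent a change from baseline.
- SAP 8.7 governs the reporting: "All the data will be summarized by cohort, and cohorts A and B combined", and "No statistical test will be performed".

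**The concern.** Category 4 puts transaminases and bilirubin in one row, but its third condition removes every subject whose ALP stayed at or below 2 x ULN. That row can read zero while subjects with both elevations exist. If the ALT/AST and bilirubin rows are both non-zero, the table leaves open whether they describe the same subjects.

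The shift tables and descriptive statistics do not close the gap, because nothing in their description combines parameters.

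A non-empty ALT/AST row is plausible. Protocol 1.3.3.3, on the study of AFM13 with pembrolizumab, reports "alanine aminotransferase increased (6 [20.0%] patients" out of 30. This is weak support: it was a combination study in Hodgkin lymphoma, no 3 x ULN threshold is stated, and nothing is said there about bilirubin.

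What is at stake is how complete the descriptive safety summary is.

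**Working it through.** The plan gives no figure to reproduce here. The check is whether the planned rows determine the joint count.

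**Notation.** a = subjects in the ALT/AST row; b = subjects in the bilirubin row; p = subjects in the ALP row; c = subjects in the combined row; J = subjects with both ALT/AST above 3 x ULN and bilirubin above 2 x ULN, counted under the same visit convention as c.

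**Identity.** J = c + (subjects with both elevations who do not also meet the ALP condition). The second term is in no planned row.

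**Bounds.** With small rows relative to N, c ≤ J ≤ min(a, b).

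**Two data sets with the same rows.** N = 103 is the Cohort A maximum in the Protocol Synopsis. All cell counts are assumed.

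| Subjects with | Set 1 | Set 2 |
|---|---|---|
| ALT/AST and bilirubin, ALP not raised | 0 | 3 |
| ALT/AST only | 5 | 2 |
| bilirubin only | 3 | 0 |
| ALP only | 2 | 2 |
| none of these | 93 | 96 |
| **Total** | **103** | **103** |
| Row a (ALT/AST) | 5 | 3 + 2 = 5 |
| Row p (ALP) | 2 | 2 |
| Row b (bilirubin) | 3 | 3 |
| Row c (combined) | 0 | 0 |
| **J** | **0** | **3 (3/103 = 2.9%)** |

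The four reported rows are the same and J differs.

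**Enumeration.** With assumed N = 100, a = 10, b = 5, p = 8, all consistent cell counts were enumerated. If c = 0, J can be any value from 0 to 5. If c = 2, J can be any value from 2 to 5.

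**Range for this trial when c = 0.** Take a between 5 and 21. The figure 21 is 20.0% x 103 = 20.6, rounded up; it is a generous upper figure for the reasons given under the concern. N = 128 for Cohorts A and B combined is 103 + 25, the Synopsis maxima.

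| Assumed b | Largest possible J | % of 103 | % of 128 |
|---|---|---|---|
| 1 | 1 | 0.97 | 0.78 |
| 3 | 3 | 2.91 | 2.34 |
| 5 | 5 | 4.85 | 3.91 |

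If a is only 2, the largest J for b = 1, 3, 5 is 1, 2, 2. In every case the smallest possible J is 0. These are limits on what the table leaves open, not expected counts.

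**Visit convention.** Once J is reported, J − c gives the subjects without ALP above 2 x ULN only if both rows use the same convention and ALP is available. Suppose the combined row needed all three elevations at one visit while the new row allowed any visits. A subject with ALT, bilirubin and ALP each raised at a different visit would count in J but not in c. Subtraction would then place that subject among those without raised ALP, although ALP was raised.

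**The case against.** The strongest reply is that this is a preference. Protocol 8.6.2.2 promises per-parameter statistics, shift tables and listings, and the SAP delivers these and adds a liver table. No objective, rule or decision in either document uses the pairwise count, and the safety endpoint in SAP 4.4 concerns treatment-related AEs. The SAP chose a three-part category, and neither document says the two-part count is the one that matters. All this stands, and it is why the point is minor. It does not alter the fact that the row excludes subjects with both elevations and that no other row restores them.

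Second, there is another hepatic output. A clinically significant joint elevation should be recorded as an AE under Protocol 5.4.7 and may then reach the hepatic TEAE table of SAP 8.7.1. That table counts reported terms, so it can show that hepatic events occurred but not how many subjects crossed both thresholds.

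Third, subjects in each category are listed, and with rows of this size the overlap is a comparison of a few subject numbers. A reader might infer that such cases would be lost or hidden. They would not be: the data are collected and listed, and only the summarized count is missing.

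Fourth, a reader might infer from the earlier ALT figure that joint elevations are likely. The documents do not support that, since they contain no figure on bilirubin or on joint elevations.

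Finally, the table templates are in a separate document (SAP 1) that was not available. They may contain the row. The SAP is where the categories are defined, so the row should be there too.

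**Conclusion.** The point holds in a limited form. As published, SAP 8.7.2 cannot report how many subjects had ALT or AST above 3 x ULN with bilirubin above 2 x ULN, because its one combined category also requires ALP above 2 x ULN and the remaining rows only bound the overlap. This follows from the definitions and does not depend on the assumed counts. The size is unknown: the documents give no expected number of such subjects, and it may be zero.

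The effect is confined to a descriptive table. A reader might take this as a flaw in safety monitoring or in a stopping decision, but safety is summarized without testing and no rule in the visible text uses the category. Nor is it a finding that a timing rule is absent. The text of SAP section 7, which covers derived variables, is not shown, so whether the three elevations must fall at one visit cannot be judged. It is a minor improvement, worth making because it costs almost nothing.

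**What to change.** In SAP 8.7.2, add one category, both summarized and listed: (ALT or AST above 3 x ULN) and total bilirubin above 2 x ULN, regardless of ALP. Use the same visit convention as the existing combined row and state that convention next to both rows. The existing row may stay. Derive the count without ALP above 2 x ULN by subtraction only under that common convention, and note any subject whose ALP is missing.

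The cost is one table row and one listing flag, from laboratory data already collected and at thresholds the SAP already uses. No assessment or clinical rule changes.
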